6.3.3.6 Follow-Up Visits

The determination of the study endpoints will require rigorous clinical follow-up and quality data collection. The Investigator or delegated study personnel will ensure the patient is scheduled for follow-up visits according to Table 6.

Table 5Follow-up Visit Windows.

| Follow-Up Visit | Visit Window (days following Procedure) |
|-----------------|---|
| 30 Day | 30 days, +14 days |
| 6 Month | 180 days +/-30 days |

| 1 Year | 365 days +/-60 days |
|--------|----------------------|
| 2 Year | 730 days +/-60 days |
| 3 Year | 1095 days +/-60 days |
| 4 Year | 1460 days +/-60 days |
| 5 Year | 1825 days +/-60 days |

The importance of attending the 30 Day follow-up visit should be discussed with the patient. Planned absences should be recorded to facilitate continued ability to contact a study patient during the course of the study. If a patient cannot be reached for a follow-up visit, the investigator will document on the follow-up data form, the efforts undertaken to contact the patient, referring physicians, including internists as well as cardiologists, family members, or other alternate contacts noted in the study patient's records. These efforts should include 3 attempts of telephone contacts at separate dates and times, and a registered letter. If a patient can no longer be located, the investigator must contact an intermediary (e.g. patient's private physician) without delay.

Patients for whom the study procedure was begun but do not receive and retain the study valve will be followed up until the 30-day assessment or resolution of any AE for safety purposes. Patients with an ongoing AE at the 30 Day visit should have AEs reassessed at 30 day window closure (day 44). These patients should then be exited from the study. In the event that the patient's implanted valve is explanted, the patient needs to be followed up until resolution of any AE for safety purposes. These patients should then be exited from the study.

6.3.3.6.1 30-Day Visit

All patients will undergo the following assessments within the 30-Day follow-up period +14 days):

- Pertinent physical examination [include blood pressure, weight and all major systems findings]
- Adverse events
- Current cardiac medications and all medications given for cardiovascular effect
- NYHA functional classification
- CSS Angina Classification
- Neurological assessments
 - o NIHSS
 - o MRS
- 6 Minute Walk Test (6MWT)
- Clinical Laboratory Test
 - o Blood count (hemoglobin, hematocrit, platelet count, white blood cells)
 - o Creatinine

- CK/CK-MB and/or troponins
- o Albumin
- 12-Lead ECG
- Comprehensive TTE. If not adequate, a TEE will be performed

For patients with abnormal findings related to valve integrity and position and patients with adverse events related to worsening valve function, fluoroscopic imaging of the implanted valve will be completed.

6.3.3.6.2 6 Month Visit

All patients will undergo the following assessments within the 6 Month follow-up period:

- Adverse events
- Current cardiac medications and all medications given for cardiovascular effect

The 6 month visit may be completed via a telephone conversation with a delegated study team member. The telephone call must be documented in the patient's study records.

6.3.3.6.3 1 Year Visit

All patients will undergo the following assessments within the 12 Month follow-up period:

- Pertinent physical examination [include blood pressure, weight and all major systems findings]
- Adverse events
- Current cardiac medications and all medications given for cardiovascular effect
- NYHA functional classification
- CSS Angina Classification
- 12-Lead ECG
- Comprehensive TTE. If not adequate, a TEE will be performed

For patients with abnormal findings related to valve integrity and position and patients with adverse events related to worsening valve function, fluoroscopic imaging of the implanted valve will be completed.

6.3.3.6.4 2-5 Year Annual Follow-up Visit

All patients will undergo the following assessments within the 2-5 Year annual follow-up period:

- Pertinent physical examination [include blood pressure, weight and all major systems findings]
- Adverse events
- Current cardiac medications and all medications given for cardiovascular effect

- NYHA functional classification
- CSS Angina Classification
- Comprehensive TTE. If not adequate, a TEE will be performed

For patients with abnormal findings related to valve integrity and position and patients with adverse events related to worsening valve function, fluoroscopic imaging of the implanted valve will be completed.

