4.1 Primary Endpoint

The primary endpoint is all-cause mortality at 30 days post-index procedure.

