6.3.3 Study Procedures

The Study Visit Schedule is outlined in Table 4 for enrolled subjects for the duration of the study from Screening and Baseline through the 30 Day visit (Primary Endpoint) and 5 year follow-up visits.

| | Screening | Baseline (≤30 days of procedure) | Procedure | Post-Procedure (Within 48 hours) | Discharge | 30 Day Follow-Up (+14 days) | 6 Month (+/-30 days) | 1 Year (+/-60 days) | 2-5 Years (+/-60 days) |
|--|-----------|-------------------------------------|-----------|-------------------------------------|-----------|--------------------------------|----------------------|---------------------|------------------------|
| Informed Consent | Х | | | | | | | | |
| Medical History | Х | | | | | | | | |
| Physical Exam | Х | | | | Х | Х | | Х | Х |
| CSS Angina | Х | | | | Х | Х | | Х | Х |
| NYHA Classification | Х | | | | Х | Х | | Х | Х |
| STS Risk Score, Logistic EuroSCORE, and EuroSCORE II | х | | | | | | | | |
| Operability Risk Assessment | х | | | | | | | | |
| Cardiac Medications | | Х | Х | Х | Х | Х | Х | Х | Х |
| Adverse Event Assessment ¹ | | | х | х | х | х | х | х | х |

Table 3 Study Visit Schedule

7 February 2017, Version 2.0

| Frailty Assessment | | Х | | | | | | |
|---|---|----------------|--------|----------------|----------------|----------------|-----------------------|-----------------------|
| NIH Stroke Scale | | X ² | | X ² | X ² | X ² | | |
| Modified Rankin Scale | | X ² | | X ² | X2 | X ² | | |
| Six Minute Walk Test (6MWT) | | х | | | | х | | |
| | | | Lab | S | | | | |
| Hemoglobin, Hematocrit, Platelet Count and White Blood Cells | | х | | х | х | х | | |
| PTT or PT/INR | | Х | | Х | Х | | | |
| CK/CK-MB and/or Troponins | | X ³ | | X4 | | х | | |
| Creatinine | | Х | | Х | Х | Х | | |
| Liver Panel (ALT, AST) | | Х | | | | | | |
| Albumin | | Х | | | | Х | | |
| | | Non | Invasi | ve Tests | | | | |
| ECG | | Х | | Х | Х | Х | Х | |
| Chest X-ray | | Х | | | | | | |
| Transthoracic Echocardiogram (TTE) ⁶ | х | | | | х | х | х | х |
| Fluoroscopic imaging implanted valve | | | х | | | X ⁵ | X ⁵ | X ⁵ |
| | | In | vasive | Tests | | | | |
| CT Thoracic/Abdomen with visualization of iliac and femoral arteries | x | | | | | | | |
| Cardiac Catheterization or CT angiogram | х | | | | | | | |
| Supra-aortic Angiogram or (TEE) | х | | х | | | | | |
| Invasive hemodynamics | | | х | | | | | |

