8.3 Adverse Event Reporting

All adverse events are reported from the start of the procedure, which is defined as when anesthesia is firsts administered, and are reported until subject participation has ended (i.e. completion of the study or withdrawal of consent). Adverse events must be reviewed at every follow-up visit until resolution, AE has stabilized (according to Investigator), or the study has been completed. Should the adverse event be ongoing at time of study completion, the database should be updated to reflect status.

Reporting guidelines for adverse events:

- Record the number of units of blood needed for any transfusion associated with any overt bleeding event
- Failure of a percutaneous closure device shall be reported as an access site vascular closure device complication
- Vascular complications shall be designated as access or non-access related;

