11.2 Timing

Study subjects will undergo screening and pre-procedure visits, and then follow-up visits at Discharge, and 30 Days (+14 days) for Endpoint analysis. Long-term follow-up data is collected at 6 Months (+/- 30 days), 1 Year (+/- 60 days), 2 Years (+/- 60 days), 3 Years (+/- 60 days), 4 Years (+/- 60 days), and 5 Years (+/- 60 days).

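### The explant rule lets a patient leave the study before day 30, although the primary endpoint is 30-day all-cause mortality

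*Combined protocol and SAP*

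**What the plan says.** The endpoint is fixed in section 4.1: "The primary endpoint is all-cause mortality at 30 days post-index procedure". Section 11.3 reports it on the AT population, which a patient enters when the first investigational device is inserted. Section 11.5 estimates it by Kaplan-Meier with Greenwood limits.

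Section 6.3.3.6 has two exit rules side by side:

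- Patients whose procedure was begun but who "do not receive and retain the study valve will be followed up until the 30-day assessment or resolution of any AE". Adverse events still open at the 30-day visit are looked at again on day 44, and the patient then leaves the study.
- For a patient whose "valve is explanted, the patient needs to be followed up until resolution of any AE for safety purposes. These patients should then be exited". No visit or day is named.

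The general text makes no exception for explant. Section 6.3.3.6.1 states: "All patients will undergo the following assessments within the 30-Day follow-up period". Section 11.2 schedules "follow-up visits at Discharge, and 30 Days (+14 days) for Endpoint analysis". Section 5 has every patient followed for five years.

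Section 11.3 gives one censoring rule, for AT patients who did not receive the valve: day 30 or the resolution of adverse events, without saying which governs. It gives none for explants.

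**The concern.** The second exit rule omits the 30-day reference that the first contains, and it is the sentence most specific to explants. A site that applies it literally can close out a patient explanted before day 30 once the adverse events have resolved, also before day 30, and has no further duty to make contact. The patient remains in the AT denominator. A death between exit and day 30 would be missing from the primary estimate.

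Section 11.5 leaves further detail to a SAP. A SAP can define how such a patient is censored, but it cannot supply vital status that nobody collected. Section 11.4 speaks only of preventing missing data.

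There is a related wording problem in section 11.3. Read literally, its choice between day 30 and adverse-event resolution allows a patient who never received the valve to be censored before day 30. The day-44 sentence in section 6.3.3.6 suggests that the later date is meant, but section 11.3 does not say so.

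**Working it through.** **Reading the passages together**

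1. An explant after the patient leaves the procedure room does not remove the patient from any analysis set. AT membership is fixed at first device insertion, and the Valve Implant set is fixed on leaving the room (section 11.3). The patient also counts toward the 60 (section 6.3.2).
2. The first exit rule need not cover such a patient, because section 11.3 ties receiving and retaining the valve to leaving the procedure room.
3. The all-patients wording of section 6.3.3.6.1 does not settle the matter. Sections 6.3.3.6.2 to 6.3.3.6.4 use the same wording for the 6-month to 5-year visits, which exited patients plainly do not attend.

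The explant sentence therefore has no day-30 floor, and the general text contradicts it without overriding it.

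**Size**

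The plan has no figure of its own to reproduce: no assumed rate, power or performance goal is given, and the 50-60 patients come from a regulatory agreement (section 11.1). The documents also give no number of early explants and no mortality after explant. The following is therefore an assumed case.

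- N = 50 or 60. The AT set could be slightly larger, since only implanted patients count toward 60.
- One patient exits on day 10 and is censored there.
- Two other patients die, either both before the exit (days 2 and 5) or both after it (days 12 and 20).

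Kaplan-Meier mortality at day 30:

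- Other deaths before the exit: 1 − (59/60)(58/59) = 2/60 = 3.33%. At N = 50 it is 2/50 = 4.00%.
- Other deaths after the exit: 1 − (58/59)(57/58) = 2/59 = 3.39%. At N = 50 it is 2/49 = 4.08%.

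| | N = 60 | N = 50 |
|---|---|---|
| Reported | 3.33% to 3.39% | 4.00% to 4.08% |
| Truth if the exited patient dies by day 30 | 3/60 = 5.00% | 3/50 = 6.00% |
| Reported too low by (points) | 1.61 to 1.67 | 1.92 to 2.00 |
| Truth if the exited patient survives | 2/60 = 3.33% | 2/50 = 4.00% |
| Reported too high by (points) | 0 to 0.06 | 0 to 0.08 |
| Greenwood 95% half-width, 1.96 × SE (points) | 4.54 to 4.62 | 5.43 to 5.54 |

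With no other deaths, the plan would report 0% with a Greenwood standard error of 0, where full follow-up gives 1/60 = 1.67% or 1/50 = 2.00%.

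**Expected effect of one such exit**

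Let r be the risk of death between exit and day 30. The expected understatement is (2 + r)/N minus the reported rate. Two values of r are used: 3.4%, the full 30-day TAVI mortality that section 2.2.2 cites from PARTNER Cohort A, and 10%, an assumption with no source in the documents.

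| r | N = 60 (points low) | N = 50 (points low) |
|---|---|---|
| 3.4% | 0.00 to 0.06 | −0.01 to 0.07 |
| 10% | 0.11 to 0.17 | 0.12 to 0.20 |

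A negative value means that the reported rate is too high. For example, at N = 50 and r = 10%, 2.10/50 − 2/50 = 4.20% − 4.00% = 0.20 points.

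**The case against.** The best defence is that the explant sentence only releases patients from long-term follow-up and sets a safety minimum, while the 30-day visit text, which names all patients and follows directly, still applies. That reading is possible. It has to be supplied by the reader, however, and it is weakened because the same words are used for visits that exited patients do not attend.

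The second argument is rarity, and it stands. The affected patient must leave the room with the valve, be explanted before day 30 and have every adverse event resolved before day 30, in a population at high surgical risk. Under section 8.3, adverse events are reviewed at each follow-up visit until resolved or stable, and the next scheduled visit after discharge is day 30, so an event open at discharge would normally be checked then. The number affected may well be zero.

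It also stands that Kaplan-Meier accommodates censoring, so the endpoint remains calculable, and that no hypothesis or performance goal exists, so no decision can reverse. The direction of any bias is not documented either, since exit at adverse-event resolution may select patients who have recovered. The 3.4% is a rate for the whole 30 days in another trial, so it is not a true lower bound for risk after day 10.

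None of this removes the contradiction. It limits how much the contradiction matters.

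**Conclusion.** The concern holds and is minor. Followed as written, the explant sentence can leave day-30 vital status uncollected for a patient in the primary analysis population. One missed death costs about 1/N, or 1.6 to 2.0 points, which is well inside the Greenwood half-width of 4.5 to 5.5 points. The expected effect of one early exit is at most about 0.2 points, and it is close to nil if the patient survives. These sizes rest on the assumed exit day, the two other deaths and the residual risk. The contradiction itself rests only on the text.

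**What to change.** Reconcile the explant sentence in section 6.3.3.6 with section 6.3.3.6.1, and align section 11.3 with both:

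- State in sections 6.3.3.6 and 11.3 that vital status is ascertained through at least day 30 for every AT patient, including those not implanted and those explanted.
- State in section 11.3 that censoring before day 30 happens only on withdrawal or loss to follow-up, at the last date the patient was known to be alive. This replaces the present choice between day 30 and adverse-event resolution.

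The cost is one or two sentences by amendment and a few extra vital-status contacts up to day 30. From the sponsor's side, the only drawback is that the reported mortality could turn out slightly less favourable.

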6.3.4 Missed Visits

Every patient should be encouraged to remain in the study until they have completed the protocol-required follow-up period. If the patient discontinues prematurely from the study, the reason for discontinuation must be documented on the appropriate case report form (CRF). Possible reasons for premature discontinuation may include, but are not limited to the following:

- Withdrawal of consent: Patient decides to withdraw from the study. If a subject withdraws from the clinical investigation, the reason(s) should be recorded. If such withdrawal is due to problems related to the investigational device safety or performance, the investigator shall ask for the subject's permission to follow his/her status/condition outside the investigation.
- Lost to follow-up: All patients should be encouraged to return to the clinic for evaluation during follow-up (excluding 6 Month telephone visit). If a patient is unable to return to the clinic, 3 separate telephone calls should be made to attempt to bring the patient back into the clinic or obtain safety information. All attempts should be documented in the source documents. If the patient does not respond to the 3 telephone calls then the Investigator should send a certified letter to the subject.

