11.5 Endpoint Analysis

Patient data listings and tabular and graphical presentations of results will be provided. All clinically relevant baseline and follow-up variables will be tabulated. Descriptive statistics will be used for continuous variables (e.g., mean, standard deviation, sample size, minimum, and maximum) and frequency tables or proportions for discrete variables.

Kaplan Meier estimates will be performed at the pre-specified follow-up times to project the estimates for time-related safety endpoints. The Kaplan-Meier analysis will be used to compute the 30-day mortality rate, the primary endpoint; the standard error and confidence limits will be computed using Greenwood's algorithm.

Echocardiographic data will be analyzed by an Echo core laboratory with respect to the degree of total aortic valve regurgitation (TVR) and paravalvular aortic valve regurgitation (PAR) according to the VARC-2 definitions [46].

These data and other categorical data (e.g., NYHA class) will also be presented as shift from baseline for each of the pre-specified follow-up periods.

More specific information regarding the statistical analysis will be presented in the Statistical Analysis Plan (SAP).

12. Study Administration

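### The plan has no route for a death after withdrawal of consent to reach the all-cause mortality analysis, and seeks permission for later status checks only when the device is the reason

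*Combined protocol and SAP*

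**What the plan says.** Section 4.1 sets the endpoint: "The primary endpoint is all-cause mortality at 30 days post-index procedure". Section 11.5 sets the method: "The Kaplan-Meier analysis will be used to compute the 30-day mortality rate, the primary endpoint", with Greenwood confidence limits. The same method serves the time-related safety endpoints at the scheduled follow-up times, and section 5 plans 5 years of follow-up for everyone.

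Section 6.3.4 treats withdrawal of consent and loss to follow-up as two separate reasons for leaving. For withdrawal it makes two requests. The first applies to all: "If a subject withdraws from the clinical investigation, the reason(s) should be recorded". The second is limited by reason: "If such withdrawal is due to problems related to the investigational device safety or performance, the investigator shall ask for the subject's permission". What is then asked for is "permission to follow his/her status/condition outside the investigation".

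Section 8.3 says that adverse events "are reported until subject participation has ended (i.e. completion of the study or withdrawal of consent"; a death would be reported as one of these.

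Patients who cannot be reached or cannot return are handled differently. Sections 6.3.3.6 and 6.3.4 provide telephone calls, a letter and contact with family and physicians, and in the end "the investigator must contact an intermediary (e.g. patient's private physician) without delay".

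Section 11.4 is about preventing missing data and gives no handling rule. The only censoring rule, in section 11.3, concerns treated patients who did not receive the valve. Section 11.5 leaves further detail to an SAP, and the text supplied contains nothing more on withdrawal.

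**The concern.** Death from any cause can be ascertained with little effort and does not require the patient to attend visits. It should be known for as many treated patients as possible, whether or not they stay in the study and whatever reason they give for leaving.

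Here the one stated request is narrow, and its product sits outside the study data. A patient who formally withdraws is therefore censored on that date. Kaplan-Meier then assigns that patient the risk of those who remain. This is harmless if withdrawal is unrelated to prognosis. It understates mortality if patients in decline are the ones who withdraw. The study has one arm, so no comparator would share such an error, and section 2.1 says the data are for regulatory approval. With at most 60 implanted patients, a single death is a visible part of the result.

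**Working it through.** **1. The plan's own figure.** Sections 1 and 11.1 attribute the 50-60 patients to a regulatory agreement. No alpha, power, margin or dropout rate is given, so there is nothing to reproduce. The only related arithmetic is the gap in section 5 between 60 implanted and 50 completing 30 days: (60 - 50)/60 = 16.7%. The plan does not call this a dropout allowance.

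**2. Where a death would go, by type of exit.**

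| Exit | Status sought? | Stated route to the mortality analysis? |
|---|---|---|
| Cannot be reached or cannot return | Yes: calls, letter, contacts, intermediary | Yes, participation has not ended |
| Withdraws because of the device | Permission is asked | None: follow-up is outside the study, and 8.3 has closed reporting |
| Withdraws for another reason | Not stated | None: 8.3 has closed reporting |

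The last two rows end in the same place. On the text as written, both groups are censored at withdrawal.

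**3. Thirty days, illustration.** Inputs: N = 60 (section 5 maximum, used here as the analysed number). Deaths d = 2, since 0.034 × 60 = 2.0, with 3.4% being the TAVI arm's 30-day mortality in the high-risk randomised cohort cited in section 2.2. Using that rate here is an assumption. The number of withdrawals of unknown status, w, is also assumed.

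- Best case: d/N.
- Worst case: (d + w)/N.
- Kaplan-Meier: between d/N (all censored after the deaths) and d/(N - w) (all censored before them).
- Width of the unknown range: w/N, so 1/60 = 1.7 points per patient.

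| w | Kaplan-Meier | Possible range |
|---|---|---|
| 1 | 3.3-3.4% | 3.3-5.0% |
| 3 | 2/60 to 2/57 = 3.3-3.5% | 2/60 to 5/60 = 3.3-8.3% |
| 5 | 2/60 to 2/55 = 3.3-3.6% | 2/60 to 7/60 = 3.3-11.7% |
| 10 | 2/60 to 2/50 = 3.3-4.0% | 2/60 to 12/60 = 3.3-20.0% |

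The last row uses the whole gap from step 1 and is a ceiling, not a forecast. For scale, the exact 95% interval for 2/60 is 0.4% to 11.5%. That interval describes sampling error and does not cover unknown status.

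**4. Five years, illustration.** Take the 44.2% 3-year TAVI mortality quoted in section 2.2 for the earlier SAPIEN valve, and assume a constant hazard: λ = -ln(1 - 0.442)/3 = 0.194 per year. In-study 5-year mortality, which Kaplan-Meier estimates, is 1 - exp(-5λ) = 62.2%. Let ω be the yearly withdrawal rate, r the ratio of the death hazard after withdrawal to that before it, and a = λ + ω. True survival at T = 5 is

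exp(-aT) + ω·exp(-rλT)·[1 - exp(-(a - rλ)T)]/(a - rλ).

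| ω per year | Withdrawn by 5 years | r = 1 | r = 2 | r = 3 |
|---|---|---|---|---|
| 2% | 6.1% | 62.2% | 63.5% | 64.2% |
| 5% | 14.4% | 62.2% | 65.3% | 67.0% |
| 10% | 26.2% | 62.2% | 67.9% | 71.0% |

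The last three columns give true 5-year mortality against a Kaplan-Meier value of 62.2% throughout. With r = 1 there is no bias at any withdrawal rate. Otherwise the gap runs from 63.5 - 62.2 = 1.3 points to 71.0 - 62.2 = 8.8 points. The documents give neither ω nor r.

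**The case against.** A reader might infer that mortality is biased by the stated reason for leaving. The documents do not support that. It would need deaths found after device-related withdrawal to be counted while others are not. Section 6.3.4 places the former outside the study and no section brings them back in, so the reason makes no difference to the estimate.

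A reader might also infer that deaths after other withdrawals are discarded by rule, or that favourable bias is established. Section 6.3.4 is silent on other withdrawals: it neither requires nor forbids asking. Bias needs informative withdrawal, and nothing in the documents shows that sicker patients withdraw.

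The affected group is also narrow. Stroke, a long hospital stay or transfer home is not in itself withdrawal of consent. Patients who simply cannot attend fall under the tracing rules, sites are trained to seek information from other sources (section 12.5), and monitors check attempts to trace lost patients (section 12.6).

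Finally, the primary analysis is descriptive, with no margin to cross. All named endpoints are at 30 days, when formal withdrawal is plausibly rare, and one missed death (1.7 points) is small beside an interval of 0.4% to 11.5%. The consent form was not available and might already permit vital-status checks.

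All of this stands and limits the point. It does not supply the missing route: tracing is for patients who are lost or unable to return, and permission in a consent form would not by itself say that the data are collected or counted.

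**Conclusion.** The gap is real and confined to formal withdrawal of consent. Followed as written, the plan neither records nor counts a death after such a withdrawal, and it holds nothing with which to check the assumption that Kaplan-Meier then makes. This is an unprotected and uncheckable risk, not a demonstrated bias, and its size cannot be known from the documents.

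At 30 days, each unknown status is worth 1.7 points if 60 patients are analysed. The expectation that few will arise by then is an assumption. The exposure is larger in the long-term mortality figures, although those are not named endpoints and the 5-year illustration rests on an assumed constant hazard, withdrawal rate and hazard ratio. The point does not call the design into question. It is worth acting on because the remedy is inexpensive and protects the primary endpoint.

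**What to change.** In section 6.3.4, replace the device-only request with one made to every patient who withdraws, whatever the reason: permission to collect vital status by telephone, from the treating physician or from records, through 5 years. Record the answer and the status in the eCRF as study data, and amend section 8.3 so that its end of reporting does not shut this out.

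In section 11 or the SAP, state that deaths learned this way enter the mortality analysis, including the primary endpoint if they occur by day 30. State that patients who refuse are censored at withdrawal. Report a best/worst-case sensitivity analysis for them, with d/N and (d + w)/N as the limits at 30 days. Make sure the consent form allows all this.

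The cost is a short protocol change, matching consent wording if it is not already there, one eCRF field and occasional calls. Telephone contact is already accepted for the 6-month visit. Some patients will still refuse, and reported mortality may rise slightly.
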